11. STATISTICS AND ANALYSIS

11.1. Statistical Analysis Plan (SAP)

The plans for the statistical analysis of the study are outlined below. There will be a separate SAP document in use for the trial with a more detailed description of the planned analysis.

11.2. Outcome variables

The primary outcome variable is whether an escalation in current treatment for PsA is required. An escalation in treatment consists of one or more of the following:

- Increase in dose of current medication
- Increase in frequency of dose administration
- Change in route of administration (i.e. from oral to sc MTX if dose not reduced)
- Initiation of a new medication in addition to existing therapy (including steroid >5mg prednisolone, conventional, targeted synthetic, or biologic DMARD)
- Initiation of a new medication as a switch from existing therapy (including steroid >5mg prednisolone, conventional, targeted synthetic, or biologic DMARD)

Reduction of therapy will also be collected, defined as any of the following:

- Decrease in dose of current medication
- Decrease in frequency of dose administration
- Change in route of administration, where not covered as described under “Escalation” above
- Stopping a medication

If the patient is retained on the same treatment regimen as they were on before the clinic visit, this will be considered as “No change”

Details of treatment prior to (at the start of) the appointment and subsequent to the appointment (including any treatment changes) will be collected.

Secondary outcomes comprise the following:

Patient data:

- PsA impact of disease (PsAID-12) scores
- Patients' satisfaction with consultation as measured by the COLLABORATE scores
- Perceived efficacy on patient-physician interaction score (PEPPI)
- Other assessments performed (see 9.7) will be used for the analysis of factors affecting treatment decisions but do not represent outcomes per se

Physician data:

- Physician's opinion of the reasons driving the treatment decision
 - Assessment of tender/swollen joints/enthesis
 - Assessment of skin and nail psoriasis
 - Marker of systemic inflammation (e.g. CRP)
 - Routine patient reported outcomes (e.g. patient global or pain scores)
- Physician's opinion of how the PsAID-12 questionnaire responses influenced the treatment decision today.

11.3. Description of the Statistical Methods

A stratified estimate of the percentage of patients requiring an escalation in PsA treatment will be derived, with clinic as the stratum. For the primary outcome, logistic regression will be used to investigate the effect of the total PsAID-12 score on the probability of modifying treatment, after adjusting for clinic. This analysis will not take account of other possible predictive factors: see later paragraph in this section. The odds ratio will be estimated for unit increases in PsAID-12 score with associated 95% confidence interval.

Logistic regression will be used to investigate the relationship between various factors and the decision to change treatment. Potential factors to be investigated include:

- Patient characteristics (gender, disease duration, comorbidities, including presence of fibromyalgia)
- Physician characteristics (age)
- Disease activity characteristics (Patient global, physician global, joint counts, BSA, enthesitis, dactylitis)
- Disease impact characteristics (PsAID-12, Patient pain, HAQ, SF-36)

Various logistic regression models will be fitted to the data to identify the factors having most influence on the decision to escalate treatment. Once a suitable model has been identified, the term for PsAID-12 will be added to see its effect on that model. This will be done by assessing the goodness of fit of the models with and without PsAID-12, and also by estimating the odds ratio associated with a unit increase in PsAID-12 score, after fitting other predictive terms.

The collaboRATE scores will be used to assess the degree of patients' satisfaction with their consultation and the relationship between these scores and the decision to change treatment, and other key outcomes, will be investigated in summary tables and/or graphs.

The PEPPI scores will be used to assess the patients' own perceived level of confidence in interacting with the physician during the consultation. The relationship between these scores and the decision to change treatment, and other key outcomes, will be investigated in summary tables and/or graphs.

The characteristics of the patient population with regard to demographics, severity and duration of PsA and HRQoL, and characteristics of the participating centres (age/sex of physicians, country and type of centre), will be summarised in tables.

Other variables will be summarised in tables of descriptive statistics.

The study team will do a detailed review of all the physicians' reports of the use of PsAID-12 in order to identify emerging themes. These will be summarised and reported on qualitatively. For example, themes may include the value of insight provided by the PsAID-12 and the balance between the extent of pain and patients' ability to cope.

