6. OBJECTIVES AND OUTCOME MEASURES

Objectives	Outcome Measures	Timepoint(s) of evaluation of this
------------	------------------	------------------------------------

		outcome measure (if applicable)
Primary objective		
Assess the influence of PsAID-12 score on likelihood of treatment escalation	PsAID-12 questionnaire Treatment escalation recorded in clinic, with reason for decision	Cross-sectional
Secondary objectives		
Evaluate the impact of reviewing the PsAID-12 questionnaire on the physician's decision to change treatment	Likert scale "Beyond your usual clinical assessment, how did your review of the patient's PsAID-12 questionnaire responses impact on your therapy decision for this patient"	Cross-sectional
Assess the effects of other factors that influence the likelihood of treatment escalation	Treatment escalation in clinic Factors include patient gender, disease duration, comorbidities, physician age, disease activity and PROs. Specifically addressing the impact of PsAID-12 individually and above other factors	Cross sectional
Determine which factors physicians feel influence treatment decisions in routine practice	NRS of the perceived importance of individual factors that may influence individual treatment decisions	Cross sectional
Evaluate patient satisfaction and perceived patient efficacy in the consultation and examine how this links to PsAID-12 score and change in treatment	CollaboRATE and PEPPi questionnaires and their relationship to PsAID-12 scores and treatment change	Cross sectional
Explore the physicians' views on the use and value of the PsAID-12 tool	Qualitative reports by physicians with themes identified retrospectively	

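### The primary outcome is defined as escalation, but the primary model in 11.3 is worded for any modification of treatment, and 11.9 and 11.12 name the outcome as change

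*Combined protocol and SAP*

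**What the plan says.** The primary objective in Section 6, repeated in the synopsis, is "Assess the influence of PsAID-12 score on likelihood of treatment escalation". Section 11.2 agrees: "The primary outcome variable is whether an escalation in current treatment for PsA is required". It lists what qualifies ("An escalation in treatment consists of one or more of the following"), then treats reduction as something else ("Reduction of therapy will also be collected, defined as any of the following"), with an unchanged regimen as a third category. Section 7 describes the same three-way record.

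Section 11.3 begins with escalation: "A stratified estimate of the percentage of patients requiring an escalation in PsA treatment will be derived". The next sentence, which specifies the primary model, changes the term. It models "the effect of the total PsAID-12 score on the probability of modifying treatment, after adjusting for clinic".

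The factor models show the same split. The secondary objective is "Assess the effects of other factors that influence the likelihood of treatment escalation". Section 11.3 introduces these models as examining "the relationship between various factors and the decision to change treatment", and after the list of candidate factors it describes them as finding what drives escalation.

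Section 11.9 labels the primary outcome, in brackets, as a change in therapy. Section 11.12 says outright that it is treatment change.

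Section 11.4 justifies a planning rate of 30% by a cited study of 503 patients in which 32% had a treatment change, most of it escalation. No exact share is given.

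**The concern.** In this plan, modification is a wider category than escalation, because a reduction also modifies treatment. Two analysts could follow the protocol, code patients with only a reduction in opposite ways, and report different primary odds ratios. Under the literal wording of 11.3 the odds ratio would describe the likelihood of any change in regimen, which is not the objective. Leaving the event open until the data are in also leaves room for a choice made after seeing results.

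The planning rate raises a lesser, related question. The number of factors that 500 patients can support depends on the number of escalations, but the rate used to justify it comes from a study of any change.

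**Working it through.** **Which patients are coded differently.** Using the categories in 11.2:

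- Regimen unchanged: non-event under either wording.
- At least one escalation item, with or without a reduction item: event under either wording, because one qualifying item is enough for escalation.
- Reduction only: non-event under escalation, event under modification.

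The two outcomes therefore differ only in the reduction-only patients. If there are none, the two analyses are identical. If there are some, the effect on the odds ratio depends on how many there are and how reduction relates to PsAID-12. The documents give neither, so no figure for the shift can be derived.

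**The plan's own calculation for PsAID-12 (11.4).** Inputs: 30% rising to 40% per SD, 95% power, two-sided alpha 5%, stated n about 316.

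- OR = (0.40/0.60)/(0.30/0.70) = 1.556; ln OR = 0.4418; squared = 0.19522.
- Hsieh formula: n = (1.960 + 1.645)² / [p(1−p)(ln OR)²].
- At p = 0.30: 12.995 / (0.21 × 0.19522) = 317.0, so 317. The plan's 316 is reproduced to within rounding.

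**The plan's factor count (11.4).** 15 factors × 10 events = 150 events; 150/0.30 = 500 patients. This is also reproduced.

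**What the cited 32% implies for escalation.** Read the majority as more than half and at most all of the changes:

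- Lower limit of the rate: 0.32 × 0.5 = 0.16 (exceeded). Upper limit: 0.32 × 1 = 0.32.
- Escalations in 500 patients: more than 500 × 0.16 = 80, up to 500 × 0.32 = 160.
- Factors at 10 events each: about 8 to 16, against 15 planned.
- For the escalation rate itself to reach 30%, 0.30/0.32 = 93.75% of the changes would have to be escalations.

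**Does a lower escalation rate threaten the primary test?** Hold the OR at 1.556 and use the same formula:

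- At p = 0.16: 12.995 / (0.1344 × 0.19522) = 495.3, so 496 patients for 95% power.
- Power with 500 patients at p = 0.16: √(500 × 0.1344) × 0.4418 − 1.960 = 1.66, which gives about 95%.

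The planned 500 is therefore just enough even at the lower limit. Like the plan's own calculation, this formula has no term for clinic.

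**The case against.** The strongest reply is that 11.3 contains only a loose verb. The model sentence is introduced as concerning the primary outcome, which 11.2 has defined, and the sentence before it is about escalation. The hypothesis in Section 5 also speaks of intensification. This largely stands: escalation is the better reading. It does not close the matter, because 11.4 speaks of treatment being modified for the quantity it bases on an any-change rate, and 11.12 states the wider outcome without qualification.

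A second reply is that 11.4 treats the terms as equivalent. It passes from change to escalation within one worked example (the 50% case), its PsAID-12 calculation is in terms of intensifying, and the factor-count paragraph names intensification as its event. This stands too. A reader might infer that 11.4 leaves the event of these calculations undefined, but the text does not support that. What remains is narrower: the 30% has no stated source other than an any-change rate. Section 11.4 also already accepts that a rate below 30% would support fewer factors.

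Third, 11.9 and 11.12 specify no model. That is correct, and they need only consistent wording.

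Fourth, 11.1 and 11.9 defer detail to a separate SAP, which was not available for this review and may settle the coding. Even so, the protocol's sections would still disagree with one another.

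**Conclusion.** The inconsistency is real and should be fixed, because it concerns the event in the primary model. Escalation is almost certainly intended. If 11.3 is applied as written, reduction-only patients become events and the odds ratio does not estimate the stated objective.

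Two stronger conclusions are tempting, and the documents support neither. One is that the primary odds ratio would be diluted by some given amount. That needs a reduction rate and an association with PsAID-12, neither of which is given, and there may be no shift at all. The other is that the study is too small for its primary test. At the plan's own odds ratio, power is about 95% or more across the whole range of escalation rates that the cited figures allow.

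The quantified consequence is confined to the secondary factor models: about 8 to 16 factors rather than a secure 15. That range assumes that the cited 32% carries over to this population, that majority means more than half, and that escalation in the cited study matches the definition in 11.2. The last is uncertain: 11.2 counts a switch to a new medication as escalation, so changes not classed as escalation in the cited study need not be reductions here. If the true escalation rate is 30% or more, there is no shortfall.

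**What to change.** - **11.3:** state the event of the primary model and of the factor models as escalation, as defined in 11.2, versus no escalation (no change or reduction). Report reductions descriptively.
- **11.9 and 11.12:** name the primary outcome as treatment escalation.
- **11.4:** say that the 30% is taken from an any-change rate, and that the number of factors examined will follow the observed number of escalations.
- **Optional:** tabulate visits that meet both the escalation and the reduction lists. Section 11.2 already classes them as escalations, so nothing depends on it.

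The cost is a few sentences. No extra patients, visits or data items are needed, since 11.2 already collects treatment before and after the appointment.

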The hypothesis is that the use in clinics of the PsA impact of disease (PsAID-12) questionnaire, specifically knowledge of the overall score and information from the various impact sub-domains, will influence the decision to apply treatment intensification in routine practice. We believe that the routine use of PsAID-12 questionnaires will enable a better understanding by clinicians of the impact of disease on their patients, will improve physician-patient communication and influence treatment interventions. A secondary aim of this study is to evaluate patient satisfaction with their clinician interaction when the PsAID-12 questionnaire is used and whether it is related to treatment change.

Obviously, treatment decisions for individuals are complex and will be based on many different factors. To investigate this further, we will use regression modelling to identify the key factors, in addition to PsAID-12 scores, that may be associated with treatment changes (particularly escalation), including physician characteristics, patient characteristics, inflammatory disease activity and patient reported outcomes.

This study will use routine implementation of the PsAID-12 questionnaire, using the freely available GRAPPA App, to support an increased understanding by clinicians of the physical, social and psychological impact of psoriatic arthritis (PsA) on their patients' lives, and see if this is related to treatment decisions and patient satisfaction. The study will also seek to learn about the Clinician's views on the value of PsAID-12 as a tool for in their practice both in terms of whether they considered its use impacted on their treatment decision for individual patients and also to collect their overall feedback on the tool.

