11.12. Bias

The study is observational and not randomised, so is subject to various types of bias. Selection bias can occur through the type of patients invited to participate at each centre, or in the choice of participating centres.

Study centres are to be selected based on the potential population size, the ability to perform the study, and variety of hospital/clinic settings to provide a cross-section of different clinics. At each centre, a random subset of eligible patients presenting at routine clinics each month during the study time frame will be invited to participate. This is to try and avoid subjective decisions by the physicians as to who they invite to join the trial. A log will be kept of those who do and do not agree to participate to see whether the refusal rate is similar across all participating sites. A high refusal rate could lead to significant bias in that the recruited patients may not reflect the general PsA population. The recruitment rates for each centre will be summarised in the study report. Demographic and other disease characteristics will be used to summarise the study population across sites to see whether they are consistent and to assess the extent to which they reflect the general PsA population.

The primary outcome of the study is treatment change, which is by definition, a subjective choice. The study investigators will be asked to make treatment decisions based on the information available to them, as they would usually do. Since the aim of the study is to assess the influence of PsAID-12 on the decision, care must be taken not to unduly influence participating physicians as to what factors they should consider when making any treatment decisions.

The various PRO instruments will be completed by the patients themselves to avoid any possible influence by research staff at the study sites. In particular, questionnaires assessing the level of satisfaction with the consultation (i.e. PEPPi and COLLaBORATE) will be done by the patients alone, with the completed forms collected by study staff so that they are not seen by the physicians as this could affect the way that patients respond.

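### The primary question, the influence of PsAID-12 on escalation, is answered by an odds ratio adjusted for clinic only, which disease activity can confound; the conclusion is not tied to the planned adjusted analysis

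*Combined protocol and SAP*

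**What the plan says.** The hypothesis in section 5 is that using PsAID-12 in clinic "will influence the decision to apply treatment intensification in routine practice". The primary objective in section 6 is to "Assess the influence of PsAID-12 score on likelihood of treatment escalation", and section 11.12 repeats the thought: "Since the aim of the study is to assess the influence of PsAID-12 on the decision".

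The primary model in section 11.3 is a logistic regression for "the effect of the total PsAID-12 score on the probability of modifying treatment, after adjusting for clinic". The next sentence adds: "This analysis will not take account of other possible predictive factors: see later paragraph in this section".

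Two secondary elements go further:

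- Section 6 has an objective on other factors, "Specifically addressing the impact of PsAID-12 individually and above other factors". Section 11.3 serves it by fitting various models over a list of potential factors, and then: "Once a suitable model has been identified, the term for PsAID-12 will be added to see its effect on that model". The output is a comparison of fit with and without PsAID-12, and an adjusted odds ratio.
- Section 6 also has a physician Likert item, which begins "Beyond your usual clinical assessment, how did your review of the".

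Section 11.1 announces a separate, more detailed SAP. It is not among the supplied documents.

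**The concern.** The protocol supplies both arms of a confounding path. Section 5 reports that PsAID-12 correlates with disease activity. Section 11.4 reports that in the earlier cohort behind the sample size, 32% had a treatment change, mostly escalation for active disease. Patients with more active disease can therefore score higher on PsAID-12 and be escalated more often, even if no physician acts on the score.

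The clinic-only odds ratio cannot separate that path from influence of the questionnaire, yet it is the estimate attached to the primary objective and section 11.3 calls it an effect. The adjusted odds ratio is closer to the question, but it is secondary. The supplied text states no selection rule and forces no activity term into the model, so even that estimate is not certain to be activity-adjusted. At stake is whether a positive primary result is reported as PsAID-12 influencing decisions when it may show only that sicker patients are treated more.

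**Working it through.** **1. The plan's own figure.** Section 11.4 uses the Hsieh method for a rise from 30% to 40% per SD of PsAID-12, with 95% power and two-sided 5%.

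- Odds ratio = (0.4/0.6)/(0.3/0.7) = 1.556; log = 0.4418.
- n = (1.960 + 1.645)² / (0.3 × 0.7 × 0.4418²) = 317, against the stated 316. It reproduces, with no allowance for covariates.
- For 80% power the same formula gives 192.

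**2. How far activity alone can move the clinic-only odds ratio.** From the documents: 25 centres, 500 patients (taken as 20 per centre), 30% escalating. Assumed, because the documents give no value: activity–PsAID-12 correlation r, activity odds ratio per SD, and a clinic variance of 0.17 on the logit scale. The direct PsAID-12 effect is set to zero.

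Rough check: the clinic-only log odds ratio is about r × ln(activity odds ratio), with standard error about 0.105. At r = 0.5 and odds ratio 1.5 this is 0.5 × 0.405 = 0.203, z = 1.93, so about half of studies are significant. Simulation (2,000 studies per cell, Wald test at 0.05) gives the percentage significant:

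| Activity odds ratio per SD | r = 0.3 | r = 0.5 | r = 0.7 |
|---|---|---|---|
| 1.5 | 23 | 49 | 80 |
| 2.0 | 47 | 89 | 99.6 |
| 3.0 | 81 | 99.5 | 100 |

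The median clinic-only odds ratio runs from 1.13 to 2.08 per SD and exceeds the planned 1.556 in three of the nine cells. With activity fitted, 5% to 7% are significant.

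**3. Which adjusted model.** The assumptions here are five physician-assessed measures (tender and swollen counts, enthesitis, dactylitis, BSA) with odds ratio 1.25 each and correlation 0.35 with PsAID-12, and patient global and pain correlated 0.6 to 0.7 with PsAID-12. If patient global and pain also drive the decision (odds ratio 1.15 to 1.25 each), then with zero direct PsAID-12 effect the percentage significant is:

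- five measures only: about 28% to 55% (26% to 70% over a wider set of assumed correlations);
- backward selection at p < 0.05 over all eight covariates, one possible reading of section 11.3: about 8% to 9%;
- all eight covariates forced in: about 4% to 7%.

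**4. Price in power.** Hsieh's adjustment is n/(1 − R²), where R² is the share of PsAID-12 variance explained by the covariates. With 500 patients, 95% power for 1.556 holds up to R² = 1 − 317/500 = 0.37, and 80% up to 1 − 192/500 = 0.62. In the assumed cells the eight covariates explain 0.52 to 0.66. Power is Φ(√(500 × (1 − R²) × 0.21) × 0.4418 − 1.96), which gives 88% at 0.52 and 75% at 0.66. Adding clinic terms lowers this: simulated power is about 69% to 75% (62% to 79% over the wider set).

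The five-measure model reaches 94% or more in the same runs. Where patient global and pain drive decisions, part of that figure is their effect credited to PsAID-12.

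**5. Events per term.** Eight covariates plus PsAID-12 make 9 terms, or 90 events by the plan's rule of 10, against 150 expected. With 24 clinic contrasts there are 33 terms, and 150/33 = 4.5 events each.

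**The case against.** The strongest reply is that the plan hides nothing and already contains most of the remedy. The omission is stated in section 11.3, with a pointer to the adjusted analysis. Section 5 accepts that decisions rest on many factors, and sections 2 and 5 also use the weaker wording that PsAID-12 may be related to decisions. All of this stands. What remains is the gap between the word *influence* and the model attached to it.

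Four stronger readings are tempting, and the documents do not support them.

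- *The primary analysis has an inflated false-positive rate.* It does not, for what it estimates. Where activity drives both, the within-clinic association is truly non-zero. The percentages above matter only if the result is read as influence.
- *Data-driven selection is itself the damage.* Under one assumed selection rule it did nearly as well as forcing in all eight covariates. The defect shown is the absence of any guarantee and of any link to the conclusion.
- *A short model with the five physician-assessed measures is the natural cure.* Section 11.3 itself lists patient global and physician global as disease activity. Section 5 cites rheumatoid arthritis research in which 60% of treatment change related to patient-reported outcomes, and step 3 shows how that model then fails. Nor is there good ground to set physician global aside as rated after PsAID-12 is seen: section 9.7 lists it before the patient-reported outcomes, although it does not say when the physician sees the score.
- *The covariates are fixed nowhere.* The separate SAP may fix them.

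**Conclusion.** The point holds in this form: the clinic-only odds ratio is a sound within-clinic association, but it cannot carry a conclusion about the influence of PsAID-12, and the supplied text does not tie that conclusion to the adjusted odds ratio or the Likert item. With no direct effect, it would be significant in about 23% to 100% of studies over the assumed range, against 5% to 7% with activity fitted. The direction follows from the protocol's own statements. The size rests on correlations and odds ratios that the documents do not give, so the range is wide.

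A reader might infer that adjustment would then isolate the effect of using the questionnaire. It would not: section 9.6 provides no comparator, and the adjusted figure remains association beyond measured factors. This is an improvement worth making, not a fatal flaw.

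**What to change.** 1. Report the clinic-only odds ratio as a within-clinic association, and drop *effect* and *influence* from its description.
2. Base any statement about influence, or about PsAID-12 beyond other factors, on the adjusted odds ratio already planned in section 11.3, read with the Likert item. Force in that section's own activity list (tender and swollen joint counts, enthesitis, dactylitis, BSA, patient global, physician global) plus patient pain. Show the model without the two globals and pain as a sensitivity analysis, because these may overlap PsAID-12. Do not rest the claim on that smaller model alone.
3. State that, with no comparator, even the adjusted odds ratio is association beyond measured factors and not the effect of using the questionnaire.

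The cost is wording and precision. Section 9.7 already collects every variable, and no patients are added. The interval widens, and power for 1.556 per SD is about 69% to 75% under the assumed correlations. BSA is recorded in categories and may need more than one term. With so few events per term, a conditional fit stratified by clinic is worth considering: in simulations of the five-measure model it estimated a true 1.556 as 1.57 to 1.58, against about 1.61 with clinic as fixed terms.

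If the separate SAP already fixes the adjusted model, only items 1 and 3 and the link to the primary conclusion remain.

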11.4. Sample Size Determination

The initial sample size calculation was based on the need to estimate the percentage of patients for whom treatment is modified, with a stated degree of precision. This was defined as a 95% confidence interval for the percentage with width 10 percentage points (e.g. 25% to 35% for a percentage of 30%). This is based on data from the GRACE study which recruited 503 patients worldwide and found that 32%

underwent a treatment change, the majority escalation for active disease (Helliwell et al, ARD 2013; 72: 986). For a percentage of 30% (i.e. 30% of patients requiring treatment change), a study of 333 patients would have 80% power to estimate a percentage of 30% requiring change with a confidence interval of $\pm 5\%$ (Source: SAS® PROC POWER). A larger percentage of patients needing treatment change or a more precise estimate (narrower confidence interval) would require a larger sample size. For example, if the proportion requiring treatment escalation is 50%, then 390 patients would be required for the study to have at least an 80% chance of obtaining a 95% confidence interval of width 10 percentage points (i.e. 45% to 55%).

In order to investigate the effect of the total PsAID-12 score on the proportion, the sample size can be calculated using the method in Hsieh (1998). For example, if the effect of an increase in 1 s.d. of the PsAID-12 score is to increase the chance of intensifying the treatment from 30% to 40%, approximately 316 patients would be required for power of 95% and two-sided alpha of 5%

For the secondary outcome of assessing the importance of the various factors on an event (in this case the decision to intensify treatment), a rule of thumb is 10 patients experiencing the event per factor. If 15 factors affecting the decision to change treatment are to be investigated then this would require at least 150 patients requiring a treatment change, which for a percentage of 30% would need 500 patients in total. If the percentage requiring a treatment change is less than 30% then reliable estimates of the effect of fewer factors could be derived. Conversely, with a frequency of treatment change closer to 50% of patients, the effects of more factors could be estimated. It is likely that there could be some missing data but this will be checked carefully at source sites. There is no follow up required for this cross-sectional study so we have not accounted for loss to follow up.

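### Section 11.3 searches for the factor model and estimates it in the same 500 patients, so weak factors that survive will look too strong and ordinary 95% intervals for them will under-cover

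*Combined protocol and SAP*

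**What the plan says.** Section 11.3 gives a list of potential factors (patient, physician, disease activity and disease impact characteristics) and then states: "Various logistic regression models will be fitted to the data to identify the factors having most influence on the decision to escalate treatment". The next step is: "Once a suitable model has been identified, the term for PsAID-12 will be added to see its effect on that model". PsAID-12 also appears in the factor list itself: "Disease impact characteristics (PsAID-12, Patient pain, HAQ, SF-36".

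The primary analysis is separate. It regresses the treatment decision on PsAID-12 with adjustment for clinic, and section 11.3 says of it: "This analysis will not take account of other possible predictive factors: see later paragraph in this section". The only 95% interval that section 11.3 promises belongs to this analysis: "The odds ratio will be estimated for unit increases in PsAID-12 score with associated 95% confidence interval".

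Section 11.4 ties the sample size to the factor analysis. Its starting point is "a rule of thumb is 10 patients experiencing the event per factor", from which it reasons: "If 15 factors affecting the decision to change treatment are to be investigated then this would require at least 150 patients requiring a treatment change". At its assumed 30% rate of change, this comes to the planned 500. It also expects factor effects to be estimated reliably, with fewer factors if treatment change is less common than 30%. Section 11.1 leaves further detail to a separate SAP, which is not part of the supplied text.

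**The concern.** When the data choose the model, a weak factor is kept mainly in those samples where its estimate happens to be large. The estimate is then reported given that it passed, so it is biased away from 1. The usual standard error takes the model as fixed and ignores the search. Correlation makes this worse, because closely related measures compete and chance helps decide which one stays. Patient global, pain and HAQ are all patient-reported measures of one disease, so some correlation is to be expected, although the documents give no figure.

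The secondary objective on other factors affecting escalation is at stake. Some of the factors reported as drivers of treatment decisions, and the strength given to the weaker ones, could be products of the search.

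**Working it through.** **The plan's own figure.** Required N = factors × events per factor ÷ event rate = 15 × 10 ÷ 0.30 = 500. This reproduces. The other calculations in section 11.4 ask for 333, 390 and 316, so only the 15-factor calculation reaches 500.

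**A reference for a strong factor.** Section 11.4 assumes that one SD of PsAID-12 moves the proportion from 30% to 40%. OR = (0.40/0.60) ÷ (0.30/0.70) = 1.556, and ln OR = 0.442. The Hsieh formula gives N = (1.960 + 1.645)² ÷ (0.30 × 0.70 × 0.442²) ≈ 317, against the stated 316. An OR of 1.56 per SD is therefore what the plan itself treats as a realistic, well-powered effect.

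**Main simulation.**
- From the documents: N = 500, 30% events, 15 candidates.
- Assumed: standardised factors with true ORs per SD of 1.56 (two factors), 1.3 (two), 1.2 (two), 1.1 (four) and 1.0 (five), and a common pairwise correlation of 0, 0.3 or 0.5.
- Assumed selection rules: backward elimination at p<0.05, backward at p<0.157 (AIC-like), or a univariable screen followed by backward at p<0.05.
- 1500 runs per setting, without clinic terms.

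Coverage of nominal 95% intervals, pooled over retained factors:

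| Rule | Correlation 0 | 0.3 | 0.5 |
|---|---|---|---|
| Backward, p<0.05 | 88.6% | 80.7% | 73.9% |
| Backward, p<0.157 | 91.0% | 87.7% | 84.9% |
| Screen, then backward | 90.2% | 80.8% | 73.9% |

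The full 15-factor model without selection covers 94.6% on average, with mean log odds ratios 1.03 to 1.07 times the truth.

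By true effect, over all rules and correlations:

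| True OR per SD | Coverage when retained | Mean log OR ÷ true log OR |
|---|---|---|
| 1.56 | 91% to 96% | 1.02 to 1.26 |
| 1.3 | 85% to 97% | 1.14 to 1.74 |
| 1.2 | 76% to 95% | 1.39 to 2.37 |
| 1.1 | 53% to 89% | 2.2 to 4.1 |

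A null factor kept at p<0.05 has an interval that excludes 1 by construction, so its coverage is 0%. At p<0.157 it is 60% to 67%. On the odds ratio scale, a true 1.1 would be reported as about exp(2.2 × 0.0953) = 1.23 to exp(4.1 × 0.0953) = 1.48.

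**Two further simulations with other assumptions.**
- 14 candidates plus PsAID-12, a two-factor correlation structure, and log ORs of 0.1 to 0.4 per SD. Pooled coverage was 68% with backward p<0.05, 84% with an AIC-type threshold and 94.6% in the full model. For a true log OR of 0.2, the mean retained estimate was 0.40 to 0.49, that is, 2.0 to 2.45 times the truth.
- Backward p<0.05 compared with a full model that included 25 clinic terms. Retained factors covered 70% to 90%, with log ORs inflated 1.6 to 2.6 times at a true OR of 1.2. The full model covered 94% to 95%.

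**PsAID-12 itself.** When it is forced in after a backward search of 14 other factors, its interval covers 93% to 94.5% (full model 93% to 94%), and its mean OR is 0% to 6% too high. The primary model involves no search.

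**The case against.** The strongest reply is that the plan promises no 95% intervals for the factor odds ratios and names no selection method, and that the separate SAP may supply both. That stands as far as it goes: backward elimination is an assumption here, and the effect on intervals applies only if ordinary ones are reported. It does not remove the point. Section 11.3 commits to a search on the study data and section 11.4 expects factor effects to be estimated. Naming a rule would not by itself correct the estimates that follow from it.

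The second reply is that the sizes rest on assumed effects, correlations and rules. That also stands, so they are given as ranges. Pooled coverage is also pulled down by retained null factors.

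Third, the 15-factor sentence in section 11.4 is conditional, and investigating 15 candidates is compatible with selecting among them. A reader should not infer that the plan is committed to a full 15-factor model. It remains true that this is the calculation that leads to 500.

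Fourth, a reader might infer a contradiction because PsAID-12 is both in the factor list and added last. The paragraph after the list explains its role: it is investigated by adding it to the chosen model. A clearer wording is enough.

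Finally, a full model with clinic terms might seem too large for about 150 events. The simulation with 25 clinic terms still gave 94% to 95% coverage.

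**Conclusion.** The concern holds for weak factors in the secondary factor analysis. With 500 patients and 30% events, retained factors had pooled coverage of about 68% to 91%, and log odds ratios for true ORs of 1.1 to 1.2 were inflated about 1.4 to 4 times. These ranges rest on assumed effect sizes, correlations and selection rules.

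Two stronger readings are not supported. One is that all the factor intervals fall far below 95%. Strong factors cover 91% to 96%, and pooled coverage with independent factors is 89% to 91%. The other is that surviving factors look two to three times too strong. That figure belongs to particular scenarios and to the log odds scale, not to the odds ratio. Nor does the problem reach the PsAID-12 conclusions: the primary odds ratio is untouched and the adjusted one nearly so. This should be changed before analysis, but it does not threaten the primary result.

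**What to change.** Replace the search with one pre-specified logistic model.

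- **Closed list.** Use the section 11.3 factors that are actually collected under sections 8.1 and 9.7. SF-36 is listed but not collected, so it drops out. Counting tender and swollen joints separately and BSA as one term, and leaving PsAID-12 out of the base model, 14 factors remain. PsAID-12 makes 15. BSA is recorded in categories, so state how many terms it takes.
- **Clinic.** Adjust for clinic as in the primary model. Physician age then draws on sites with more than one physician, so say how it will be handled.
- **Size limit.** Rank the list in advance and cut it at observed escalations ÷ 10. For example, 150 escalations support 15 factors. If only 25% escalate (an assumed rate), 500 × 0.25 = 125 supports 12. This matters because the 32% cited in section 11.4 is any treatment change, not escalation alone.
- **Reporting.** Give every odds ratio and 95% interval from this model, without selection. Then add PsAID-12 and compare the two nested models by a likelihood-ratio test on the same patients.
- **Reduced models.** Label any such model exploratory, with bootstrap inclusion frequencies and optimism-corrected fit.

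The cost is protocol and SAP wording and some analysis time, with no extra patients or data. Intervals for correlated factors will be somewhat wider.
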